5.1. General Statistical Methods

For continuous measures, descriptive summary statistics will include the number of observations, mean, standard deviation, median, minimum, maximum, as well as the number of eyes with results not reported. For continuous measures analyzed as changes from earlier visits, the 95% confidence interval for change will also be reported. Continuous measures may also be dichotomized or otherwise split into clinically meaningful categories and additionally analyzed as categorical measures.

For categorical measures, the percentage and number of cases for each condition (e.g., 20/20 or better) will be reported. The number of eyes without results will be omitted from the numerator and denominator of such calculations (i.e., no imputation will be performed).

Any calculated p-values will be based on nominal calculations with no adjustment for multiplicity.

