The CVM-00001 study is designed as a prospective, multi-center, cohort study. Any pre-planned formal hypothesis tests for this feasibility study are not for the purposes of generating definitive conclusions to support regulatory approval.

The study was carried out at five investigational centers, in the Philippines (3 centers), Panama (1) and Mexico (1).

The study comprises patients with planned removal of cataracts (cortical, nuclear, subcapsular, or a combination) by manual phacoemulsification. The investigator will determine if the test lens is to be implanted in OD, OS, or OU based on target refraction and the best interests of the subject.

All patients will have visits scheduled for 1 Day, 1 Week, and 1 Month following primary cataract extraction. During follow up the Investigator and Subject will decide if an optic exchange in the study eye is in the best interests of the subject based on refractive outcome and target. Subjects with satisfactory outcomes, or those opting not to pursue an optic exchange, will be entered into Cohort 1.

Subjects who opt for an HMIOL optic exchange in their primary eye will be entered into Cohort 2. Optic exchange patients will have visits scheduled for 1 Day, 1 Week, and 1 Month following the optic exchange procedure. These subjects may be followed up beyond 1 month as deemed necessary by the surgeon.

Several cohorts of subjects are specified to help characterize the clinical significance of the study outcomes in eyes with and without optic exchange. These cohorts are defined as follows:

All HMIOL Eyes Cohort: Defined as all study eyes implanted with the study device.

Cohort 1: Defined as the subset of study eyes implanted with the study device without a subsequent optic exchange procedure.

Cohort 2: Defined as the subset of study eyes implanted with the study device with a subsequent optic exchange procedure. Analysis of follow-up visits for this cohort will cover two separate time periods:

- Pre-Optic Exchange, comprising visits following primary cataract extraction, prior to the optic exchange visit (through 1 month).
- Post-Optic Exchange, comprising visits following optic exchange. The baseline for the post-optic
 exchange visits is the last pre-optic exchange visit (1-month).

Separate analyses are planned for each cohort.

Rev.02, 1 March 2018 Confidential Page 3 of 8

Document: TDOC-0056125 **Version:** 1.0; CURRENT; Most-Recent; Effective

Status: Effective

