5.3. Accountability

Accountability will be based on eyes (not subjects). The number and percentage of eyes available for analysis at each time point will be presented. For eyes not available for analysis, a breakdown will be provided to summarize the following reasons for missing data: subject discontinued, missed study visit but seen later, missed study visit but subject accounted for (i.e., contacted), and lost-to-follow-up. Eyes for active subjects at a time point, defined as those enrolled but who have not yet reached the corresponding time point, will also be summarized. Accountability as a percentage will be calculated based on the total number available for analysis over the total number of subject eyes enrolled minus total number discontinued and the total number active.

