5.6. Effectiveness Endpoints

Effectiveness endpoints will be summarized in the per-protocol population for each cohort at each study visit for which they are available. See Appendix A for a listing of scheduled assessments by visit.

Rev.02, 1 March 2018 Confidential Page 4 of 8

Document: TDOC-0056125 **Version:** 1.0; CURRENT; Most-Recent; Effective

Status: Effective

Protocol CVM-00001 Statistical Analysis Plan

ClarVista Medical, Inc.

Effective Date: 24-Jun-2019

6. Sample Size

The sample size for this study was not based on any statistical criteria. The sample size was chosen to provide sufficient experience and feedback regarding the ClarVista HARMONI™ Modular Intraocular Lens System at five investigative centers.

7. Analysis Populations

Safety Population: Eyes with attempted study lens (HMIOL) implantation, (successful or aborted after contact with the eye). The intraoperative and postoperative AEs and device deficiencies, slit lamp examination, dilated fundus examination, and IOP will be summarized based on the safety population.

Per-Protocol Population: Eyes with successful HMIOL implantation that do not have major protocol deviations (such as improperly enrolled in the study or lens power calculation errors). The effectiveness endpoints will be summarized based on the per-protocol population.

10. Interim Analyses

There are no plans for formal interim analyses for the purposes of study modification or possible early termination. Any interim analyses will be administrative in nature and results will not be distributed to Investigators or subjects to prevent bias from exposure to accruing study results.

Interim Safety Summary: Safety outcomes will be evaluated when all eyes in Cohort 1 and Cohort 2 have completed the 1 Month Visit following primary cataract extraction and optic exchange, respectively (post-optic exchange for Cohort 2).

Final Safety and Effectiveness outcomes will be evaluated when all study subjects complete the final visit or exit the study.

11. Deviations from the Statistical Analysis Plan

Any deviations from the Statistical Analysis Plan will be noted and described with appropriate statistical and clinical rationale as needed.

12. References

1. ISO 11979-7:2014 Ophthalmic implants — Intraocular lenses — Part 7: Clinical investigations.

Rev.02, 1 March 2018 Confidential Page 5 of 8

Document: TDOC-0056125 **Version:** 1.0; CURRENT; Most-Recent; Effective

Status: Effective

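### The SAP plans eye-level 95% confidence intervals for change without saying whether one or both eyes of a bilaterally implanted subject enter, or how their correlation would be handled

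*SAP*

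**What the plan says.** SAP 5.1 plans one kind of interval: "For continuous measures analyzed as changes from earlier visits, the 95% confidence interval for change will also be reported". It also allows for tests: "Any calculated p-values will be based on nominal calculations with no adjustment for multiplicity". It names no interval formula.

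The SAP's units are eyes:

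- Section 4 begins its cohort list with "All HMIOL Eyes Cohort: Defined as all study eyes implanted with the study device" and defines Cohorts 1 and 2 as subsets of those eyes.
- The per-protocol population in section 7 is "Eyes with successful HMIOL implantation that do not have major protocol deviations". The safety population is also a set of eyes.
- Section 5.3: "Accountability will be based on eyes (not subjects").

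Section 4 lets the investigator decide whether the lens is "implanted in OD, OS, or OU based on target refraction and the best interests of the subject". The Protocol Synopsis says the same.

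Other text suggests one study eye per subject. SAP section 4 also assigns cohorts by subject: "Subjects who opt for an HMIOL optic exchange in their primary eye will be entered into Cohort 2". Protocol 3.2.1, 3.2.4 and 3.3.6 refer to a primary eye, and 3.3.2 to surgery in the study eye. Protocol 4.9.2 records fellow-eye surgery as a concomitant procedure, and the assessment schedules have one primary operation and one set of visit forms. The Synopsis describes Cohort 1 once as eyes and once as subjects. No available text defines the primary eye or says how it is chosen in a bilateral subject.

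**The concern.** Two eyes of one person share biometry, surgeon, healing and examiner, so their changes may be correlated. An ordinary interval computed over eyes counts each eye as a separate unit of information. With positive correlation it overstates the information and comes out too narrow.

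The SAP does not say that it will treat eyes as independent; it is silent. Two programmers could follow it and produce different denominators and different intervals. SAP section 4 assigns cohorts by subject and then defines them by eye. A bilateral subject with one exchanged eye could therefore appear in both cohorts or in only one.

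This is the only interval estimate planned in the SAP text available. Means, counts and percentages at eye level carry no interval and are not affected. The point applies to whatever change summaries are produced in the All HMIOL Eyes Cohort and Cohort 1. It applies to Cohort 2 only if both eyes of a subject can enter there.

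**Working it through.** **Inputs.** Up to 200 subjects (Protocol 3.1), so at most 400 study eyes. The plan states no SD, power, interval width or bilateral count, so there is no figure of its own to reproduce. Two quantities are assumed and varied: *p*, the share of subjects implanted in both eyes, and *r*, the between-eye correlation of the change score. Protocol 3.1 has cataract extraction in each eye, but that does not by itself put the study lens in each eye, so it does not fix *p*.

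**Formula.** Take *N* subjects, *pN* of them bilateral, and equal variance σ² in all eyes. The number of eyes is *M* = *N*(1 + *p*). Then

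- Var(eye-level mean) = (σ²/*M*) × DE, with DE = 1 + 2*pr*/(1 + *p*);
- independence width ÷ correct width = 1/√DE;
- true coverage of the independence interval = 2Φ(1.96/√DE) − 1.

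**One case in full.** *p* = 0.5, *r* = 0.5: DE = 1 + 2 × 0.5 × 0.5/1.5 = 1.333. The width ratio is 1/√1.333 = 0.866, so the interval is 13.4% too narrow. Coverage is 2Φ(1.96/1.155) − 1 = 91.0%.

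**Coverage (%) of a nominal 95% interval that treats eyes as independent:**

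| Bilateral share | r = −0.2 | 0.1 | 0.3 | 0.5 | 0.8 |
|---|---|---|---|---|---|
| 10% | 95.4 | 94.8 | 94.4 | 93.9 | 93.3 |
| 25% | 95.9 | 94.5 | 93.6 | 92.6 | 91.2 |
| 50% | 96.5 | 94.2 | 92.6 | 91.0 | 88.7 |
| 100% | 97.2 | 93.8 | 91.4 | 89.0 | 85.6 |

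At *r* = 0.5 and shares of 10%, 25%, 50% and 100%, DE is 1.091, 1.200, 1.333 and 1.500, and the interval is too narrow by 4.3%, 8.7%, 13.4% and 18.4%. At *r* = −0.2 it is too wide by 1.9%, 4.3%, 7.4% and 11.8%. With a 5% share, coverage stays at or above 94.1% for *r* up to 0.8. If *p* or *r* is zero, DE = 1 and nothing changes.

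**Simulation** (200 subjects, 40,000 runs per setting). At *r* = 0.5 the eye-level t interval covered 93.9%, 92.5%, 90.7% and 89.1% for the four shares. All 20 settings in the table were within 0.4 points of the formula. An interval with subject-clustered robust variance around the same eye-level mean (factor *N*/(*N* − 1), t on *N* − 1 df) covered 94.7% to 95.2% throughout. With 30 subjects and *r* = 0.5, the independence interval covered 92.6% (25% share) and 89.2% (100% share); the clustered one covered 94.8% and 95.1%.

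**When every subject has one eye.** The clustered variance is [*N*/(*N* − 1)] × Σ(residual²)/*N*² = *s*²/*N*. With *N* − 1 df this is exactly the ordinary t interval.

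**The case against.** The strongest objection is that harm needs several conditions together, and the documents establish none of them: change summaries outside a one-eye Cohort 2, a meaningful number of bilateral subjects, analysis of their second eyes, an independence formula, and positive correlation. No endpoint is named as a change. The only change baseline the SAP defines is for post-exchange Cohort 2, where entry goes by the primary eye. UCDVA has no pre-operative measurement, so it cannot have a change from pre-op. The single-eye wording makes the 50% and 100% rows less plausible; at 5% to 10% bilateral and *r* = 0.5, coverage is 94.4% to 93.9%. SAP sections 8 and 9 could hold a relevant provision. The study is descriptive, and prescribing one variance estimator may be a matter of preference.

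Most of this stands as a limit on size. The effect may be small or nil, and no decision rule depends on it. It does not remove the gap. SAP section 2 says its analyses supersede the protocol's, and its cohort and population definitions are by eye with no limit per subject. The eyes-versus-subjects contrast in SAP 5.3 matters only if the two counts can differ. The method for an interval belongs in 5.1, where it is promised. The Synopsis passage naming subjects is a visit schedule and weak evidence alone, but SAP section 4 mixes the two units itself. A mixed model would also be acceptable; what is needed is a method that respects the subject.

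**Conclusion.** The concern holds in its conditional form. The SAP promises eye-level intervals for change, permits bilateral implantation and, in the text available, settles neither which eyes enter nor how correlated eyes are handled. If both eyes enter, are treated as independent and correlate positively, the intervals are too narrow and any p-values too small. For *r* from 0.1 to 0.8 and bilateral shares from 10% to 100%, true coverage runs from 94.8% down to 85.6%. Share and correlation are assumptions, and equal variance across eyes is assumed throughout. Zero share or zero correlation gives no effect; negative correlation gives intervals that are too wide. The consequence is misstated precision in a descriptive study, not a wrong decision. It should be corrected because the remedy is cheap and loses nothing if every subject turns out to contribute one eye.

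**What to change.** In SAP 5.1, state whether one or both eyes of a bilateral subject are analysed. Reconcile this with the bilateral option, the primary-eye wording, and the eye-based and subject-based cohort definitions.

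- **If one eye:** name it by a rule that does not use outcome data.
- **If both:** keep the eye-level mean, but compute intervals for change and any p-values with a subject-clustered robust variance (for example GEE with independence working correlation, factor *N*/(*N* − 1), t on *N* − 1 df, *N* = subjects) or a subject-level bootstrap. Where no subject is bilateral, use the ordinary t interval.
- **In either case:** report subjects and bilateral subjects beside eyes for each cohort.

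The cost is one or two SAP sentences and a little programming. No new data are needed, and the sample size stays as it is. If both eyes are kept, the eye-level means do not change; a one-eye rule would drop second eyes from them. With positive correlation the clustered intervals are wider than independence intervals: at *r* = 0.5 by 4.4%, 9.5%, 15.5% and 22.5% for bilateral shares of 10%, 25%, 50% and 100% (√DE − 1). At the higher shares that is a visible widening, and it is the precision the data support.

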5.2. Baseline Data

Data on enrollment, demographics (gender, race, age, implanted eye), and baseline characteristics of study eyes (IOL Power, pre-operative BCDVA, MRSE) from the pre-op visit will be summarized with descriptive statistics.

5.3. Accountability

Accountability will be based on eyes (not subjects). The number and percentage of eyes available for analysis at each time point will be presented. For eyes not available for analysis, a breakdown will be provided to summarize the following reasons for missing data: subject discontinued, missed study visit but seen later, missed study visit but subject accounted for (i.e., contacted), and lost-to-follow-up. Eyes for active subjects at a time point, defined as those enrolled but who have not yet reached the corresponding time point, will also be summarized. Accountability as a percentage will be calculated based on the total number available for analysis over the total number of subject eyes enrolled minus total number discontinued and the total number active.

5.4. Safety Endpoints

Safety endpoints will be summarized at each visit using the Safety population (all eyes with attempted implantation):

- Device deficiencies
- Adverse Events (AE) and Serious AEs including secondary surgical Interventions.

Other safety outcomes include surgical complications, ≥ 2 lines loss of BCDVA from a prior post-op visit, persistent corneal stroma edema, IOP increase requiring intervention, and iritis requiring treatment.

5.5. Other Safety Measures

Other safety outcomes such as slit lamp examination, intraocular pressure and dilated fundus examination, will be summarized descriptively at each visit for the Safety Population. Line listings for abnormal findings for individual eyes will be provided. Summary tables of adverse events will be provided with intra-operative adverse events tabulated separately. Intra-operative adverse events are defined as those with an onset date equal to the date of the procedure. A line listing of non-ocular serious adverse events will be provided by subject.

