#### 3.3.2 Day 0 Visit (Primary Cataract Extraction Surgery)

Prepare the subject for surgery in the study eye and review inclusion/exclusion criteria to ensure subject still qualifies to participate.

The principal investigator will perform the cataract surgery and implant the Harmoni Modular IOL.

Once the subject is confirmed stable post-surgery, provide standard post-operative instructions and discharge.

Record any AEs, adverse device effects (ADEs), unexpected adverse device effects (UADEs), or device deficiencies (DD) (see Sections 6.1.1, 6.1.2, 6.1.3, or 6.1.4 respectively) observed pre-, intra-, or post-operatively.

In the event the subject is not implanted with an HMIOL device due to an intra-operative complication, the subject will be discontinued (see Section 4.5).

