#### 3.3.4 COHORT 2: OPTIC EXCHANGE VISIT

The Investigator will carry out the optic power determination, surgical procedure, and HMIOL optic exchange.

Rev.03, 7 January 2016 Confidential Page 16 of 32

**Document:** TDOC-0056124 **Version:** 1.0; CURRENT; Most-Recent; Effective

Status: Effective

CLARVISTA MEDICAL PROTOCOL CVM-00001 REV.03

Once the subject is confirmed stable post-surgery, provide standard post-operative instructions and discharge.

Following successful completion of HMIOL optic exchange, the subject is entered into Cohort 2. Record any AEs, ADEs, UADEs, or DDs (see Sections 6.1.1, 6.1.2, 6.1.3, or 6.1.4 respectively) observed pre-, intra-, or post-operatively.

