#### 6.0 Adverse Events

Safety assessments include ocular adverse events, all serious adverse events, and adverse device events. The reporting time period is from the time of consent through the last study visit (1 Month Visit post-primary cataract extraction for Cohort 1 and post-optic exchange for Cohort 2).

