#### **Study Protocol**

- Allergic reaction to dilating drops
- Lens remnants following surgery
- Capsular tear during surgery to implant study device

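### SAP 5.5 identifies intra-operative AEs by calendar date alone, so same-day pre- or post-operative events would be tabulated as intra-operative and the rate may be overstated

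*SAP*

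**What the plan says.** SAP 5.5 states the output: "Summary tables of adverse events will be provided with intra-operative adverse events tabulated separately". It then gives the rule: "Intra-operative adverse events are defined as those with an onset date equal to the date of the procedure". The rule has no clock time, surgical phase or investigator attribution, and it does not say which procedure is meant.

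SAP Section 7 assigns AEs to the Safety Population and names two kinds: "The intraoperative and postoperative AEs and device deficiencies". The SAP therefore treats intra-operative and post-operative events as different things.

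Protocol 3.3.2 has sites record events at the Day 0 visit that are "observed pre-, intra-, or post-operatively". Protocol 3.3.4 repeats the instruction for the optic exchange visit ("Record any AEs, ADEs, UADEs, or DDs"), with the same three phases. On the AE window, Protocol 6.0 says: "The reporting time period is from the time of consent through the last study visit".

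**The concern.** The protocol recognises three phases on the day of surgery, and the SAP's rule merges them under the name of one. A reader of a table headed intra-operative will take it to describe what happened during the operation. Under the rule it describes the whole calendar day.

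This matters more than usual here because the lens has two components assembled inside the eye, and exchange of the optic is its distinguishing feature. Events during those two operations are of direct interest. The study is descriptive, so its tables are its results, and a row whose content does not match its label affects what is reported.

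**Working it through.** The plan states no intra-operative rate, expected AE rate or sample size calculation, so there is no figure to reproduce. The check is first logical, then one of scale.

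**Step 1. Can a reportable AE fall on the procedure date but outside the operation?**

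- Before surgery: yes. AE reporting starts at consent (Protocol 6.0), and the pre-operative visit window extends to Day 0 (Protocol 3.3.1). Protocol 6.2 lists "Allergic reaction to dilating drops" among events linked to the study protocol. This shows that such an event is reportable, not that one will occur on Day 0.
- After surgery: yes. Protocol 3.3.2 provides for a period before the subject leaves: "Once the subject is confirmed stable post-surgery, provide standard post-operative instructions and discharge". The first scheduled post-operative visit is on Day 1–2, so an event that begins between the end of surgery and midnight carries the procedure date.
- The same reasoning applies to the optic exchange visit.

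**Step 2. Does anything in the documents separate these events from true intra-operative ones?** No. The SAP gives no onset time, phase field or attribution rule. The AE evaluation criteria in Protocol 6.2.1 (classification, diagnosis, severity, relationship, outcome, treatment) contain no phase item.

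**Step 3. Direction.** If onset dates are accurate, an event during a procedure carries that procedure's date and is counted. Only extra events can enter. If *m* same-day events are not intra-operative, the intra-operative count is too high by *m*, the count of other AEs is too low by *m*, and the total is unchanged. This takes the rule as applied to the date of each procedure in turn.

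**Step 4. Size per misfiled eye.** Let *N* be the number of eyes in the denominator. A misfiled eye with no genuine intra-operative AE adds 1/*N*. The protocol treats up to 200 subjects and allows the lens in one or both eyes, so at full enrolment *N* lies between 200 and 400.

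- 1/200 = 0.5 percentage points
- 1/400 = 0.25 percentage points

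Fewer eyes give a larger step. A table for optic exchange alone would have a smaller denominator, which the documents do not give.

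**Step 5. Illustration.** Let *q* be the probability per eye of a same-day AE that is not intra-operative. Every value of *q* below, and the 2% true intra-operative rate, is an assumption. Eyes are treated as independent, and no eye has both kinds of event.

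Expected misfiled eyes = *N* × *q*. Chance of at least one = 1 − (1 − *q*)^*N*. Tabulated rate = 2% + *q*.

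| *q* | Expected, N = 200 | P(≥1), N = 200 | Expected, N = 400 | P(≥1), N = 400 | Tabulated rate |
|---|---|---|---|---|---|
| 0 | 0 | 0 | 0 | 0 | 2.0% |
| 0.5% | 1 | 0.633 | 2 | 0.865 | 2.5% |
| 1% | 2 | 0.866 | 4 | 0.982 | 3.0% |
| 2% | 4 | 0.982 | 8 | >0.999 | 4.0% |
| 5% | 10 | >0.999 | 20 | >0.999 | 7.0% |

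The first row is as admissible as the others. The documents do not say which applies.

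**The case against.** The strongest defence is that the rule is explicit and reproducible, and that the table is correct under it. It departs from a surgical-phase count only if a reportable same-day event outside the operation occurs. The scheduled assessments do little to bring such events to light: no intraocular pressure measurement is scheduled on Day 0 after surgery, and a pressure rise is reportable only if it needs intervention. This stands as a limit on size. It does not remove the mismatch between label and content, because both surgery visits ask for events from all three phases.

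The consequences are also limited. The study tests no hypothesis (Protocol Synopsis and 8.1). SAP Section 4 calls it a feasibility study, and no threshold or stopping rule uses this table. With accurate dates, any error makes the operation look worse, not safer. All of this stands.

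Three stronger readings may tempt a reader, and the documents do not support them.

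- *Surgical events recognised later are missed.* The rule uses onset date, not date of recognition. An event found at the 1 Day visit but correctly dated to surgery is counted. It is lost only if the site enters a wrong onset date.
- *The SAP throws away phase data that the sites collected.* Protocol 3.3.2 and 3.3.4 say which events to record. They do not show that phase is stored as a variable, and the list in Protocol 6.2.1 has no such item.
- *This table is the only evidence on surgical safety.* SAP 5.4 also lists surgical complications, device deficiencies and secondary surgical interventions, and the surgeon questionnaire covers the difficulty of implantation, assembly and exchange.

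**Conclusion.** The point holds as a misclassification built into a stated rule. A same-day pre-operative or post-operative AE would be tabulated as intra-operative, so the intra-operative rate may be overstated, by 0.5 percentage points per misfiled eye with 200 eyes or 0.25 with 400. This rests on accurate onset dates and on the rule being applied to the date of each procedure.

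A reader might go further and conclude that the reported rate will be wrong. That is not shown, because it requires at least one such event and the number may be zero. Overall AE and SAE totals are unaffected. The matter is one of labelling and interpretation in one safety table, worth correcting because the correction is cheap.

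**What to change.** In SAP 5.5, replace the date rule. Classify each AE with onset on Day 0 or on the exchange day as pre-, intra- or post-operative, using the site's record of the event or the operative record. Do this separately for primary implantation and optic exchange, and per eye, which also settles which procedure the definition refers to. Show same-day events that are not intra-operative in their own rows.

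Where phase cannot be recovered, title the table *AEs with onset on the day of the procedure*, by procedure, and do not call it intra-operative.

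The cost is a short SAP edit and a small look-up of source records for same-day AEs. SAP Section 4 describes conduct at the five centres in the past tense, so the look-up may have to be retrospective. Retitling alone needs no new data.
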